Appendix F Data Handling Rules

Appendix G Programming Codes for Statistical Analysis

1. BACKGROUND

Stroke is the fourth leading cause of death and a leading cause of disability in the United States (U.S.). More than half of all ischemic stroke patients have mild strokes at initial presentation in population-based studies (3; 10). Alteplase is the only approved therapeutic agent for the treatment of AIS (acute ischemic stroke) and is widely accepted as the standard of care for eligible patients (4; 6). The currently approved Activase® (alteplase) U.S. Package Insert (USPI) contains wording that recommends against use of alteplase in patients with “minor neurological deficit or with rapidly improving stroke symptoms” due to the fact this patient population has not been evaluated. Furthermore, the current American Heart Association/American Stroke Association Council Guidelines include “minor and rapidly improving stroke symptoms (clearing spontaneously)” as a relative exclusion criterion for alteplase (6). This is largely due to the aforementioned label wording not recommending treatment of patients with minor neurological deficit or with rapidly improving stroke symptoms (RISS), the lack of a consistent and consensus definition of who constitutes this patient population, and the absence of definitive evidence of alteplase efficacy in this setting (TREAT Task Force 2013). Therefore, this trial is designed to evaluate the efficacy and safety of alteplase in confirmed AIS patients with minor neurological deficit or with RISS, which will be referred to collectively as “mild stroke”.

For further background information see Section 1 of the protocol.

The original plan was for approximately 948 patients with mild stroke to be enrolled and randomized in a 1:1 ratio to two treatment groups. However the study enrollment was prematurely terminated due to recruitment below target in December 2016 (at approximately 1/3 of original planned enrollment of 948) and the analysis will be performed using available data from patients randomized prior to study termination.

This Statistical Analysis Plan (SAP) describes the statistical methods to be used for the clinical study report of study ML29093. This version of the SAP has been developed using version 3 of the study protocol dated 08 Jan 2015. The SAP will be finalized by [REDACTED] and approved by Genentech, Inc. before database lock and unblinding.

Statistical Analysis Plan: Alteplase—Genentech USMA
5/ML29093 5/17/2017

2. STUDY DESIGN

This is a double-blind, multicenter, randomized, Phase IIIb study to evaluate the efficacy and safety of IV alteplase in AIS patients with mild strokes that do not appear to be clearly disabling. The trial will consist of a screening assessment and randomization, treatment followed by a 30-day phone call and a 90-day follow-up visit. Treatment with the IV study drug should start within 3 hours from last known well time (stroke symptom onset).

All subjects randomized before the study was terminated will be followed to complete all assessments as originally planned.

2.1 SYNOPSIS

The protocol synopsis is provided in [Appendix A](#) and the schedule of assessments is provided in [Appendix B](#). The study flow chart is provided in [Figure 1](#) in [Appendix B](#).

2.2 OUTCOME MEASURES

2.2.1 Primary Efficacy Outcome Measures

The primary efficacy outcome measure for this study is:

- A favorable functional outcome, defined by a modified Rankin Scale (mRS) of 0 or 1 at Day 90 post randomization

All mRS assessments will be performed by investigators blinded to treatment assignment that are trained and certified in mRS administration.

2.2.2 Secondary Efficacy Outcome Measures

The secondary efficacy outcomes are measured at Day 90 and include:

- Ordinal mRS
- Global favorable recovery (Global Outcome Measure derived from mRS 0-1, National Institutes of Health Stroke Scale [NIHSS] 0-1, Barthel Index [BI] ≥ 95 , and Glasgow Outcome Scale [GOS] 1)

2.2.3 Exploratory Efficacy Outcome Measures

The following exploratory outcome measures for this study are measured at day 90 and included in the analyses described in this SAP:

- Total score of NIHSS at day 90
- Instrumental activities of daily living, as measured by the Total score of the BI at day 90
- Raw score of the GOS at day 90
- Cognition and behavior (modified 30-minute battery):
 - Controlled Oral Word Association test;
 - Hopkins Verbal Learning Test-Revised [HVLTR] trials 1, 2, and 3;
 - digit symbol coding from the Wechsler Adult Intelligence Scale III [WAIS III]; Forward and Backward Digit Span test;
 - Benton Judgment of Line Orientation test, form V;
 - HVLTR trial 4 and recognition;
 - semantic fluency [Animal Naming test];
 - Boston Naming Test [BNT; 15-item short form]
- Ambulatory performance (as measured by walking speed)
- Depression (CES-D [Center for Epidemiologic Studies, Depression]) score
- Quality of Life (EQ-5D [European Quality of Life] questionnaire)
- Stroke Impact Scale-16 (SIS-16)

2.2.4 Safety Outcome Measures

The safety outcome measures for this study are as follows:

- Symptomatic Intracranial Hemorrhage (sICH) within 36 hours of receiving IV study drug (primary safety assessment)

sICH is defined as any neurological decline attributed to new ICH seen on imaging by the investigator (based on AE reporting). New ICH seen on imaging will be later confirmed on independent reading by blinded central study radiologists
- Any ICH (based on central neuroimaging reading) within 36 hours of receiving IV study drug
- Mortality within 90 days

Statistical Analysis Plan: Alteplase—Genentech USMA
7/ML29093 5/17/2017

- Stroke-related and neurological deaths within 90 days
- Incidence, severity, and spectrum of all adverse events (AEs) and serious AEs (SAEs).

The exploratory safety measure for this study is:

- Stroke recurrence (based on AE monitoring) within 90 days

2.3 DETERMINATION OF SAMPLE SIZE

The sample size was originally determined as follows.

A sample size of 856 is required in order to achieve 80% power in the primary analysis to detect effect size of 9% absolute difference in the proportion of patients with favorable outcomes [mRS of 0 or 1 at Day 90] between the alteplase and control arms. The above power consideration assumes a control proportion of 65% and Type I error of 0.025 (one-sided), and uses a group sequential design with one interim analysis for futility (non-binding), based on O'Brien and Fleming boundary, conducted after 50% of the anticipated sample size have completed 90-day follow-up assessments. [REDACTED] was used in sample size calculation.

The intention-to-treat principle will be applied to the primary analysis and, therefore, to safeguard against dilution of the treatment effect associated with an approximate 5% non adherence rate (due to loss to follow-up, consent withdrawal, treatment crossovers and stroke mimics), the above sample size was inflated by a factor of 1.108 (5). Therefore, a total sample size of 948 was planned for this study.

The study enrollment was terminated early in December 2016, after 313 patients were randomized. The analysis will be carried out based on all available data from patients randomized prior to termination. With this sample size, power calculations show that the study will be substantially underpowered to conduct superiority tests (Table 1). Therefore, all efficacy analyses will include estimation of treatment effects with the associated two-sided 95% confidence intervals.

Table 1			
Estimated Power for the Final Sample Size (N=313)			
Assumed Effect Size	7%	8%	9%
Statistical Power ^a	25%	31%	38%
^a Based on the t-test for the observed proportions of mRS 0-1 at Day 90, using type I error of 0.025, one-sided. Assumptions are based on a blinded evaluation of non-adherences in the Jan 2017 Development Safety Update Report (DSUR) dataset: - Control response rate among confirmed strokes is 74%. - 10% of randomized subjects are stroke mimics and 80% of those stroke mimics will have favorable outcome. - 1% of subjects received concomitant tPA - 7.4% subjects without Day 90 outcome (290 effective sample size)			

2.4 ANALYSIS TIMING

One interim analysis of the primary efficacy outcome was planned for clear futility once 50% of the subjects were enrolled. The interim analysis was to be conducted according to the beta-spending approach (9) with an O'Brien - Fleming-type boundary. Because of the early termination of the study, the interim analysis will not be performed.

3. STUDY CONDUCT

3.1 RANDOMIZATION ISSUES

Due to the emergency nature of randomization in acute stroke clinical trials, treatment assignments must be made in an expeditious manner that also ensures even distribution in the treatment groups. A "step forward" randomization regimen will be used to ensure that a randomized treatment assignment is available upon patients' arrival at the hospital and treatment can initiate immediately upon signing the informed consent and eligibility confirmation (16).

This procedure will be implemented using an Interactive Web Response System (IWRS). Before the first patient is enrolled at a site, the site will register with IWRS as part of site activation and "Use Next" drug kit IDs will be allocated for the first potential patient. This assigned kit will be used to treat the first patient enrolled at the site. Next, the study site enters identification information of the patient AFTER he/she is treated (within 8 hours of initiation of the patient's study treatment). IWRS will then assign "Use Next" drug kit IDs for the next patient that becomes eligible at

Statistical Analysis Plan: Alteplase—Genentech USMA
9/ML29093 5/17/2017

that site. Randomization is triggered as soon as the “Use Next” drug kits are used to treat an eligible patient.

Allocation of the “Use Next” kits will be determined by a dynamic randomization algorithm. Particularly, allocation will be balanced within the site using the urn method (17). In case of perfect balance within site, the overall allocation will be balanced using the biased coin method (14, 15). More details are available in [Appendix C](#).

3.2 DATA MONITORING

An independent Data Monitoring Committee (iDMC) will provide ongoing review of safety outcomes and review efficacy and safety outcomes to inform a futility interim analysis after 50% of patients have completed or withdrawn from the study.

The iDMC will be composed of external advisors. The iDMC will perform functions such as:

- Review all accumulated safety data at periodic safety reviews
- Make recommendation to the Sponsor as to whether it is appropriate to discontinue the study after assessing the interim efficacy and safety data in aggregate

An independent Data Coordinating Center (iDCC) will be responsible for the preparation and review of unmasked data.

Details on iDMC membership, activities and timing are available in the Charter for the iDMC. Elaboration of the analyses that were to be conducted by the iDCC at the Interim Analysis is contained in the Interim SAP that was developed and signed-off for this study.

3.2.1 Safety Review Timing

Scheduled iDMC meetings to review safety data were planned to occur after 5% (50), 25% (237), 50% (474), and 75% (711) of patients had been enrolled or approximately annually. The last iDMC meeting prior to study termination was held on 03 May 2016, and included 225 enrolled subjects. Safety monitoring reviews included an unblinded evaluation of all adverse events (AEs), serious adverse events (SAEs), adverse events of special interest (AESI) including siCH, and any

Statistical Analysis Plan: Alteplase—Genentech USMA
10/ML29093 5/17/2017

other protocol-specified tests deemed critical to the safety evaluation of the study. However, the sponsor, investigators and other responsible for study conduct remained blinded.

4. STATISTICAL METHODS

Descriptive statistics will be produced for all endpoints. Data listings will be generated for specific endpoints as appropriate.

Categorical variables will be summarized as the number and percentage of patients or occurrences in each response category. Continuous variables will be summarized using descriptive statistics (number of observations, mean, standard deviation, median, minimum, maximum). Any required confidence intervals (CIs) will be constructed as two-sided 95% CIs.

4.1 ANALYSIS POPULATIONS

4.1.1 Intent-to-Treat Population

All randomized patients are included in the intent-to-treat (ITT) population to adhere to the ITT principle. For efficacy analyses, treatment groups will be assigned as randomized (IV Alteplase 0.9 mg/kg + Aspirin Placebo, IV Alteplase Placebo + Aspirin 325 mg).

4.1.2 Per-Protocol Population

The per-protocol (PP) population is defined as the subset of the ITT population excluding major protocol violators deemed to have the potential to affect patient outcome in terms of efficacy. No analyses will be performed for the PP population given the early enrollment termination. However, major protocol deviations will be identified in a blinded fashion prior to database lock and will be summarized. These deviations will be determined based on the medical monitors' records, as well as programmatically, using the following criteria at a minimum:

- Did not receive alteplase treatment as randomized
- Received any additional reperfusion therapy (e.g. IV or IA alteplase and/or endovascular therapy)

Statistical Analysis Plan: Alteplase—Genentech USMA
11/ML29093 5/17/2017

4.1.3 Safety Population

The Safety population is defined as all patients who received any amount of study drug. For safety analyses, treatment groups will be assigned according to the IV alteplase/alteplase placebo actually received. Thus, patients who receive active IV alteplase will be assigned to IV Alteplase 0.9 mg/kg + Aspirin Placebo group, and patients who receive IV alteplase placebo or did not receive the IV study drug (very rare) will be assigned to IV Alteplase Placebo + Aspirin 325 mg group. Group assignment will not take into account the actual dose of aspirin; however, it is expected that the majority of cases will follow the randomized treatment. Cases who did not receive treatment as randomized will be listed as described in Section 4.6.1.

4.2 ANALYSIS OF STUDY CONDUCT

The number and percentage of patients who have signed informed consent, been randomized in IWRS, received treatment, and completed through Day 30 and Day 90 (ie, completed the study) will be tabulated overall and for each treatment group. Reasons for not completing the study will also be tabulated overall and by treatment group using numbers and percentages.

A summary of the duration of the patient participation in the study will be produced. Duration will be calculated as the later date of the last efficacy or last safety assessment minus the first study drug administration date + 1.

The number and percentage of patients included and excluded from the analysis populations (ITT and safety) will be tabulated overall and for each treatment group. Reason(s) for exclusion from each population will be summarized.

Major protocol deviations will be listed and summarized by treatment group.

For those patients who are considered to have failed screening, the reason(s) for failure will be provided in a listing.

4.3 ANALYSIS OF TREATMENT GROUP COMPARABILITY

Clinically important demographic and disease characteristics at screening will be summarized overall and for each treatment group. Summaries will be produced for the ITT population.

Statistical Analysis Plan: Alteplase—Genentech USMA
12/ML29093 5/17/2017

Continuous variables will be summarized among patients with non-missing values, by the mean, standard deviation, median, first and third quartiles, minimum and maximum values. The number of patients with non-missing values will be displayed as well. Categorical variables will be summarized using numbers and percentages of patients in each category; unknown or missing will be included as a separate category.

The variables to be summarized include but are not restricted to the following:

- Demographics: sex, ethnicity, race(s), age (continuous and categorized as < 65 vs. ≥65)
- Last known well time to treatment (continuous and categorized as 0-2 hours, > 2-3 hours and >3 hours)
- Stroke characteristics: previous stroke (Y/N), RISS or non-RISS, stroke etiology, location of stroke
- NIHSS: total score (as continuous and categorical)
- Baseline substance use status: smoking and drug/substance abuse
- Medical History (MedDRA), in particular hypertension, diabetes mellitus, atrial fibrillation, and prior stroke
- Baseline Vital Signs: systolic and diastolic blood pressure and pulse
- Use of Aspirin / antiplatelet drugs within 7 days prior to screening/stroke onset
- Use of Heparin / anticoagulant drugs within 7 days prior to screening/stroke onset
- Prior medications
- Baseline neuroimaging (central reading)
- Baseline Lab Parameters: hematology (complete blood count without differential), chemistry (serum glucose), coagulation (international normalized ratio, partial thromboplastin time)

Baseline for NIHSS, vital signs and lab parameters will be defined as the last available assessment prior to initiation of any study medication.

4.4 EFFICACY ANALYSES

All efficacy analyses will be to estimate treatment effects and provide the associated two-sided 95% confidence intervals.

Statistical Analysis Plan: Alteplase—Genentech USMA
13/ML29093 5/17/2017

Endpoints based on mRS will generally use imputation to achieve the complete ITT set, with the exception of the repeated measures modeling. Other efficacy variables will use all available data in the ITT population.

Assessment of efficacy will be conducted based on endpoints collected during the Day 90 visit. The protocol allows this visit to be scheduled within 14 days of the target 90 days post-treatment; however, a wider window of 30 days will be adopted for the purpose of efficacy analysis.

More details of imputation approach for mRS are provided in Section 4.7 and Appendix D.

4.4.1 Primary Efficacy Endpoint

The primary efficacy analysis will estimate the effect of treatment with IV alteplase therapy and with the standard medical care (aspirin) in AIS patients with mild symptoms. The primary efficacy outcome is derived from the mRS.

The mRS is an assessment of disability with values from 0 (no symptoms at all) to 5 (severe disability); death will be scored as a '6'. The mRS is collected at 30 and 90 days after start of study drug administration. If death occurs prior to an assessment day (Day 30 or Day 90), the mRS will be considered available and will be set to 6.

The proportion of patients within each treatment group with a favorable outcome, defined by mRS of 0 or 1 at 90 days post-randomization, will be estimated in the IV alteplase arm and in the standard medical care arm. Reasons for not performing the assessment of mRS at Day 90 will be summarized.

The difference in proportions between the two groups will be estimated using the risk difference. The risk difference will be obtained from a linear model with the binary mRS 0-1 outcome as the response, treatment, and age, time from last known well to treatment, and baseline NIHSS as continuous covariates. Quadratic terms for the continuous covariates may be added to the model, if the Wald p-value for the quadratic term is <0.1. No interactions among the covariates will be included in this model.

A common approach for implementation of this model is binary regression, a GLM with the Bernoulli distribution for the outcome and the identity link function. This

Statistical Analysis Plan: Alteplase—Genentech USMA
14/ML29093 5/17/2017

model has a possibility of non-convergence when the estimated response probability falls outside of the (0,1) interval. To circumvent the non-convergence problem, an approach of using the ordinary least squares with a robust standard error is used in this study. It was shown that if a robust standard error is used with the ordinary least squares estimation, the estimate of the risk difference is equal or similar to the estimate from the GLM with an identity link for Bernoulli outcome approach (22, 23).

The primary efficacy analysis will include all ITT patients, with patients grouped according to the treatment assigned at randomization. Missing or out of window mRS at Day 90 will be imputed with LOCF or late Day 90 mRS, if available, or simulated with a hot deck method (see Section 4.7 for handling of missing mRS).

As a supportive analysis of the primary efficacy endpoint, unadjusted or crude risk difference will be estimated along with the two-sided 95% CI using normal approximation. The standard error for the unadjusted risk difference will be derived from the group standard errors, assuming independence:

$$SE(D) = \sqrt{\frac{p(1-p)}{N_1} + \frac{q(1-q)}{N_2}}$$

where p and q are the observed group proportions and N₁ and N₂ are the group sample sizes.

The treatment effect for the binary mRS outcome will also be evaluated using the odds ratio statistic, derived from either a logistic regression, or a repeated measures model. These are considered exploratory analyses and described in Section 4.4.3.1.

4.4.2 Secondary Efficacy Endpoints

Secondary efficacy outcomes include mRS (full scale) and global favorable recovery at Day 90. These results will further describe the treatment effect.

4.4.2.1 Ordinal Modified Rankin Scale

As a secondary endpoint, mRS at Day 90 will be further explored on the range of the values (0 to 6) where the values of 5 and 6 are grouped. The distribution of full range of mRS scores at Day 90 (imputed) will be summarized by treatment group. Both tabular displays and stacked bar charts will be prepared.

Statistical Analysis Plan: Alteplase—Genentech USMA
15/ML29093 5/17/2017

The comparison will be achieved by fitting a proportional odds model with mRS score at Day 90 as the dependent variable, and treatment group, pre-treatment NIHSS score, age, and last known well time to treatment as the continuous predictors (1, 8). Quadratic terms for the continuous covariates may be added to the model, if the Wald p-value for the quadratic term is <0.1 . No interactions among the covariates will be included in this model. The adjusted odds ratio with its two-sided 95% CI will be shown. Direction of the odds ratio will be chosen to reflect change in the odds of achieving a lower (better) mRS if treated with IV alteplase.

The proportional odds assumption will be tested by the score test, and the p-value will be reported. If the proportional odds assumption does not hold, the resulting odds ratio will not be presented. The alternative analysis planned for this situation will provide the adjusted mean difference between mRS scores with two-sided 95% CI. Methodology for this estimation is similar to the primary outcome, but using the ordinal mRS as the dependent variable.

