4.4.4 Subgroup Analyses

For the primary endpoint, consistency of treatment effect of alteplase will be evaluated by various pre-specified baseline covariates. The primary pre-specified variables and their analytic thresholds are defined by:

- Age group (< 65 vs. ≥ 65)
- Pre-treatment NIHSS score group (0-2 vs. 3-5)
- Last known well time to treatment group (0-2 hours vs. > 2 hours)
- Stroke subgroup (RISS vs. non-RISS)

Statistical Analysis Plan: Alteplase—Genentech USMA
19/ML29093 5/17/2017

Adjusted odds ratios by subgroup will be obtained from multivariable logistic regressions with the main effects for treatment, age, last known well time to treatment, and NIHSS, and fit separately for each level of the subgroup.

Interactions of IV alteplase treatment effect with each of the subgroup variables will be explored by adding interactions of the subgroup variables with treatment to the logistic regression. The interactions will be included one at a time; thus, there will be 4 separate models to test each interaction. Results from these models will not be reported, except when the interaction p-values is smaller than 0.1, in which case the p-values will be footnoted in the forest plot.

A forest plot will be constructed to visually illustrate the subgroup analyses. The plot will show the odds ratios described above with two-sided 95% CIs, corresponding to each level of these subgroups. The plot will also show the common odds ratio estimate in different color or line pattern, as a reference. A subgroup analysis will be conducted only if there is at least 10 subjects per outcome (mRS 0-1, mRS >1), and the standard error of the odds ratio estimate is stable with the addition of the covariates.

Analysis of the efficacy endpoints is summarized in [Table 2](#).

Table 2
Summary of Efficacy Analyses

Analysis	Statistical Method	Missing Data Method	Analysis Set(s)
Primary			
mRS 0-1 Day 90	Risk difference via linear regression, CI	LOCF + hot deck	ITT
Secondary			
mRS ordinal Day 90	Proportional odds model Descriptive, frequencies	LOCF + hot deck	ITT
Global outcome measure (Global test)	Logistic regression with a 4-dimensional outcome using GEE	LOCF + hot deck for mRS, non-response for death *	ITT
Exploratory			
mRS 0-1 Day 90	Logistic regression	LOCF + hot deck	ITT
	Logistic regression with Day 30 and Day 90 outcome using GEE	Repeated Measures Model (No imputation)	ITT

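### Two SAP rules let a test outcome decide what is printed: subgroup interactions appear only if p<0.1, and the ordinal mRS odds ratio is dropped if a proportional-odds test fails

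*SAP*

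**What the plan says.** **Subgroups (SAP 4.4.4).** The stated aim is to judge whether the alteplase effect on the primary endpoint is consistent across age, baseline NIHSS, time to treatment and RISS status. Subgroup odds ratios come from logistic models "fit separately for each level of the subgroup". Interactions are added one at a time: "thus, there will be 4 separate models to test each interaction". On output, the SAP says: "Results from these models will not be reported, except when the interaction p-values is smaller than 0.1". In that case the p-value goes into a footnote of the forest plot. No interaction estimate or confidence interval is planned in either case. The subgroup odds ratios do not depend on the interaction p-value: "The plot will show the odds ratios described above with two-sided 95% CIs". They need only a minimum of 10 subjects per outcome and a stable standard error.

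**Ordinal mRS (SAP 4.4.2.1).** The section first states without condition: "The adjusted odds ratio with its two-sided 95% CI will be shown". It continues: "The proportional odds assumption will be tested by the score test, and the p-value will be reported". Then comes the rule "If the proportional odds assumption does not hold, the resulting odds ratio will not be presented", followed by the replacement: "The alternative analysis planned for this situation will provide the adjusted mean difference between mRS scores with two-sided 95% CI". The mRS distribution is tabulated and charted by arm in every case. Table 2 lists the proportional odds model and frequencies for this endpoint and does not mention the fallback.

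**General aim.** After the early stop at 313 patients, sections 2.3 and 4.4 recast every efficacy analysis as estimation with two-sided 95% intervals.

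**The concern.** An estimation plan should print its estimates whatever they turn out to be. Both rules depart from that, in different ways.

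For the subgroups, the interaction is the quantity that answers the consistency question. Showing it only when its own p-value is small keeps the chance findings and hides the unremarkable results. In a trial this small a real interaction would often miss p<0.1 as well, so a missing footnote could be misread as evidence of consistency.

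For the ordinal mRS, the effect measure of a secondary endpoint is settled after the data are seen. The SAP gives no cut-off for deciding that proportional odds fails, so the choice between odds ratio and mean difference is left to whoever reads the score-test p-value. Nor does it say that the test concerns treatment only. If it is the usual joint test over all predictors, a covariate could cost the reader a treatment odds ratio that is itself proportional.

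**Working it through.** **1. The plan's own figure, for the inputs.** Table 1 is not in dispute, but its inputs are used in step 3.
- Control rate: 0.9 × 0.74 + 0.1 × 0.80 = 0.746.
- Effect after 10% mimics and 1% concomitant tPA: d × 0.9 × 0.99.
- 290 patients with an outcome, so 145 per arm; one-sided 0.025; two-proportion normal approximation.
- Power for 7, 8 and 9 points: 24.6%, 31.1% and 38.4%. Table 1 gives 25%, 31% and 38%, so the inputs reproduce.

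**2. Interactions when there is no heterogeneity.** Four tests, each printed only if p<0.1.
- Each result is hidden 90% of the time.
- If the tests are independent, all four are hidden with probability 0.9^4 = 65.6%, and at least one is footnoted with probability 1 − 0.656 = 34.4%.
- Independence is an assumption. Whatever the dependence, the chance of at least one footnote lies between 10% (the four tests coincide) and 4 × 10% = 40%.

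**3. Interactions when heterogeneity is real.** Assumptions not in the SAP: two equal halves, equal allocation, so 313/4 = 78.25 patients per cell, control rate 0.746 in both halves, unadjusted Wald test on the log-odds scale. The standard error is the square root of the sum over the four cells of 1/[78.25 p(1 − p)].
- Alteplase adds 9 points in one half and 0 in the other: the difference in log odds ratio is logit(0.836) − logit(0.746) = 0.551. The chance of p<0.1 is 26.8%, so the interaction stays hidden about 73% of the time.
- Plus 9 points in one half and minus 9 in the other: the difference is logit(0.836) − logit(0.656) = 0.983. The chance of p<0.1 is 57.9%, so it stays hidden about 42% of the time.

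**4. Ordinal mRS.** Grouping 5 with 6 leaves six levels and five cuts. A proportional-odds score test limited to treatment has 5 − 1 = 4 degrees of freedom. A joint test over the four listed predictors has 4 × 4 = 16, and more if quadratic terms enter. The SAP does not say which is meant.

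By simulation at N=313 with assumed mRS distributions and the joint test:
- If proportional odds holds, the odds ratio is withheld in about 4–6% of trials at an assumed level of 0.05 and about 9–12% at 0.10. This is simply the test level, which the SAP leaves open.
- If only age is non-proportional and treatment is fully proportional, the rate at 0.05 was about 16–18% when the age log-odds per SD moves from −0.30 to −0.90 across the cuts, and about 49–55% when it moves from −0.20 to −1.20. These slopes are invented to show the mechanism. Nothing in the SAP supports them as likely values.

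**5. The text of 4.4.2.1.** One sentence promises the odds ratio and its interval without condition; a later one withholds it. They can be read as a rule and its exception, but Table 2 records only the rule.

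**The case against.** The strongest reply is that little is really lost.

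For the ordinal mRS, the gate is a model diagnostic whose p-value is always reported, and the replacement, with its interval, is fixed in advance. The full mRS distribution is shown by arm. Adjusted odds ratios for mRS 0–1 (4.4.3.1) and mRS 0 (4.4.3.3) are planned in any event. All of that stands. A reader might infer that the odds ratio is suppressed on its own p-value. The SAP does not support this, because the treatment p-value plays no part in the rule. What the reply leaves open is the missing cut-off, the missing scope of the test, and the lack of any reason to withhold the common odds ratio rather than print it beside the alternative.

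For the subgroups, odds ratios with intervals are plotted next to the common odds ratio, and under the stated rule the absence of a footnote tells the reader that p was at least 0.1. These are exploratory analyses and no confirmatory claim rests on them. That limits the harm. But a threshold statement is not an estimate, and readers would have to approximate the interaction by hand from separately fitted models.

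A reader might also want the separate subgroup fits replaced by estimates from the interaction models, or odds ratios at every mRS cut. Neither demand is justified. The interaction model gains precision by forcing common covariate effects, which is a trade-off, and the SAP guards the separate fits with a stable-standard-error condition as well as the count of 10. At the upper cuts data would be thin: with an assumed 3% and 2% in the top two levels, about 9 and 6 of 313 patients.

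**Conclusion.** The concern holds as a reporting weakness in one secondary and one exploratory analysis. The primary estimate is not affected.

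The interaction rule is the clearer fault. It selects on the result's own p-value, never prints an interaction estimate, and conflicts with the estimation aim of section 4.4. Its size is a 34.4% chance of at least one spurious footnote under independence (10% to 40% without it). Real heterogeneity of the kinds tried in step 3 would stay hidden 42% to 73% of the time, given equal halves and a 74.6% control rate.

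The ordinal rule is milder: a pre-test that switches the effect measure, with no stated level and no limit to treatment. That a non-proportional covariate could remove the treatment odds ratio follows only if the test is the usual joint one, which the SAP neither states nor excludes. The simulated rates show that this can happen, not how often it would.

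**What to change.** **Section 4.4.4.** Print the interaction estimate, 95% interval and p-value for all four subgroup variables, on the forest plot or in a table, whatever the p-value. Keep the separate subgroup fits as planned.

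**Section 4.4.2.1.** Always present the common odds ratio with its 95% interval and name it as the lead estimate. Report the proportionality check for the treatment term. Show the adjusted mean difference in addition, not instead. Refer to the planned mRS 0 and mRS 0–1 odds ratios as the cut-specific estimates, and bring Table 2 into line.

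**Cost.** The interaction models and the mean-difference method are already specified, so the change is SAP wording and a few more output rows. The one real downside is two effect measures for one secondary endpoint, which is why the lead measure has to be named in advance.
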